9.1.3. HPV vaccine coverage in UK and in CPRD GOLD

The submitted study is in the UK, which is a country with a high Cervarix vaccine coverage. The recommended schedule in the UK for HPV vaccination of 12-13 year old girls involves three doses of Cervarix given over at least a 6-month period [DH, 2008; HPA, 2010].

In the UK public HPV immunization program (12-13 year olds), HPV vaccination coverage in the UK for 2010/11 was 89.0%, 87.6% and 83.8% for the first, second and third dose respectively [Health Protection Agency, 2012].

Vaccination records in the CPRD GOLD cover only part of the Cervarix-vaccinated population in the UK. For instance, 70.7% of the 01-SEP-1996 – 31-AUG-1997 birth cohort were reported as HPV vaccinated in CPRD GOLD versus 85.9% reported by the UK Health Protection Agency. Corresponding numbers for the 01-SEP-1994 – 31-AUG-1995 birth cohort are 70.6% versus. 81.9% (Table 2).

Table 2 HPV vaccination coverage in CPRD GOLD versus HPA-DH UK data

	CPRD† UK‡			UK‡
Birth cohort	N vaccinated	N total	%	%
01 SEP 1996 and 31 AUG 1997	16028	22685	70.7%	85.9%
01 SEP 1994 and 31 AUG 1995	16343	23143	70.6%	81.9%

† Data extracted from CPRD GOLD version ffqprd_smart_2012Q3

‡ From Health Protection Agency Department of Health [Health Protection Agency, 2012]

A first exploration of the CPRD GOLD database identified 148,731 subjects vaccinated with Cervarix between 2007 and 2010. The number of vaccinated women in the relevant age-range included in the CPRD GOLD is provided in Table 3. The number of HPV-vaccinated females in the CPRD GOLD appears to be sufficient for studying adverse events which have a low incidence after vaccination with Cervarix.

Table 3 Number of HPV-vaccinated females in the relevant age range included in the CPRD GOLD

Age range [years]	Number of subjects
[9-10]	16
[11-15]	82326
[16-20]	65080
[21-25]	866

Created by GSK Biologicals', 2012

Date extracted from CPRD GOLD version ffgprd_smart_2012Q3

9.2. Setting

Setting and study population

9.2.1. The UK HPV National Immunization Programme

The submitted study is in the UK, which is a country with a high Cervarix vaccine coverage. The recommended schedule in the UK for routine HPV vaccination of all girls at 12 to 13 years of age is [DH, 2008; HPA, 2010]:

- Vaccination at this age starts with a first dose of 0.5ml of Cervarix HPV vaccine
- The second dose of 0.5ml follows one to two months after the first dose
- A third dose of 0.5ml follows at least six months after the first dose

The UK has had sufficient Cervarix vaccination coverage to, in theory, enable data acquisition. A public immunisation programme targeting girls between 12-13 years of age including a catch-up programme for young women up to 18 years was undertaken during the academic year 2008/09. A phased catch-up programme for females born 1 September 1991 to 31 August 1995 during the 2008/09 academic year was completed by the end of the 2009/10 academic year. The programme was delivered largely through secondary schools [Crawford, 2009; Sheridan, 2009; Sheridan, 2010]. In the UK public HPV immunization program (12-13 year olds), HPV vaccination coverage in the UK for 2010/11 was 89.0%, 87.6% and 83.8% for the first, second and third dose respectively [Health Protection Agency, 2012]. The recommended age range for the UK programme matches the age range required by the FDA (9-25 years of age) for the post-licensure safety study.

The study population will be composed of female and male subjects, 9 to 25 years of age, registered in the CPRD GOLD.

The exposed cohort will be composed of female subjects vaccinated with at least one dose of Cervarix, with or without other recommended vaccines.

The unexposed historical female cohort will consist of frequency age-matched and practice region-matched female subjects from the period before the introduction of Cervarix. The unexposed concurrent male cohort will consist of frequency age-matched and practice region-matched by one-year classes (15, 16, 17, etc.) male subjects from the

period after the introduction of Cervarix. The unexposed historical male cohort will consist of frequency age-matched and practice region-matched male subjects from the period before the introduction of Cervarix.

9.2.2. Cohort identification and creation

The exposed eligible cohort have been identified based on the stepwise approach defined in Annex 5. Among eligible exposed subjects, 65,000 subjects will be randomly selected using the RANUNI function of SAS. The RANUNI function returns a number that is generated from the uniform distribution on the interval (0, 1). The corresponding subject number will be computed as *random_subj_number=ranuni(seed)*. The subjects will be ordered according the *random_subj_number* and the first 65,000 subjects will be included in the exposed cohort.

The unexposed eligible cohorts have been identified based on the stepwise approach define in Annex 5.

All the unexposed subjects who matched exposed subject for age (birth cohort) and region (frequency matching) will be identified. This represents 234 combinations of birth cohort-region (18 birth cohorts and 13 regions in CPRD GOLD). In each combination, the subjects will be randomly selected based on the distribution in the exposed cohort.

A reference date is randomly attributed to all potential unexposed subjects. For the concurrent male cohort, the reference date is a random date between 01-SEP-2008 and 31-AUG-2010. For the historical cohorts, the reference date is a random date between 01-SEP-2005 and 31-AUG-2007 (reference dates for exposed cohort – 3 years).

The random reference dates in each 'birth cohort-region" combination will be attributed randomly using the RANUNI function of SAS.

The age at reference date will be calculated for the unexposed cohort. After applying the exclusion criteria, the eligible subjects (65,000 subjects in each cohort) will be randomly selected in each of the combinations 'birth cohort-region' taking into account the distribution in the exposed cohort. The random selection will also use the RANUNI function of SAS.

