9.1.2. Rationale for study design

NOAD represent a heterogeneous group of diseases with different clinical conditions and disease progression. Some NOAD present with a chronic disease pattern of relapse over time e.g. multiple sclerosis or systemic lupus erythematous, or an acute disease pattern (e.g. Guillain Barré Syndrome).

In addition to the comparison of the exposed vs. non-exposed cohort (cohort design), the confirmed NOAD in the exposed cohort will also be analysed using a self-control case-series (SCCS) analysis.

In the cohort design, specified NOAD will be collected over a period of one year following the administration of at least one dose of Cervarix in an exposed cohort and over a comparable period in the unexposed cohorts as shown in Figure 1. Four cohorts will be constituted as shown in Figure 1. The unexposed male cohorts will be enrolled in order to assess a possible change over time in the incidence rate of NOAD in CPRD GOLD independent of Cervarix introduction. The cohorts will be frequency

116239 (EPI-HPV-040 VS UK)

Protocol FDA - EMA PASS Final Version 1 matched for the age (age class of one year) and practice region identifier at reference date (age at first dose of Cervarix).

An unexposed concurrent female cohort has been not chosen as the unvaccinated group for the following reasons:

- There is a under-reporting of HPV vaccination in CPRD GOLD as evidenced by the difference in vaccine coverage in CPRD GOLD population and the UK population (see Table 2), an exposed concurrent cohort would include both true and false unexposed subjects;
- Moreover, because of the large vaccine coverage in the UK, non-vaccinated women could have different health care behaviour compared to the vaccinated women, resulting in a difference in the probability to detect auto-immune disease.

Therefore, the reference date (time = 0) for the vaccinated (exposed) cohort will be the date of the first dose of Cervarix recorded in CPRD GOLD. The reference date for the unexposed (unvaccinated) cohorts will be a date randomly selected among the reference dates of the exposed subjects and minus 3 years for the historical cohorts.

[figure not shown]
Figure 1 Cohort design

Note: all three doses may not have been administered

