9.3.3. Data to be collected

9.3.3.1. Subjects characteristics

The following data will be extracted for the analysis population:

• Demographic characteristics: birth month and birth year, sex, region, practice region identifier, date of death (if applicable) and acceptable patient flag

- CPRD GOLD information: CPRD GOLD start date, first registration date, current registration date, registration gaps, registration status, transfer-out date, transfer-out reason
- HES information: Linkage to HES data
- Vaccines:

Administration of any other vaccine from one year before the reference date and until the end of follow-up will be collected: date of vaccination, medcodes and immunization type will be extracted from the immunisation file. Cross-tabulation of medcodes and vaccine names/class is detailed in Annex 5.

• Health care resource utilization: number of primary care resource utilization during the year before the reference date.

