9.4. Data Sources

9.4.1. The UK Clinical Practice Research Datalink General Practitioner OnLine database (CPRD GOLD)

The CPRD GOLD is the world's largest computerised database of linked anonymised longitudinal medical records from primary care. The data are drawn from the computer systems used by general practitioners (GPs) to maintain the clinical records within their practices. As of March 2011, CPRD GOLD contains records from over 12 million patients contributing 64 million person-years of prospectively recorded high-quality primary healthcare data [Williams, 2012].

The CPRD GOLD is operated on a non-profit basis by the UK Medicines and Healthcare products Regulatory Agency (MHRA), containing coded longitudinal medical records from general practices and more recently from hospital-based care (e.g., Hospital Episode Statistics, HES). The current linkage between CPRD GOLD primary care data and HES data is around 50% as of Q1 2013. The CPRD GOLD database is licensed in-house by GSK. Data quality is monitored continuously by the MHRA and practices that fail to maintain the required standards are removed from the database.

The latest update provided by the CPRD GOLD team in Q1 of 2013 (first release of 2013) contains data for 10,960,947 research standard patients, drawn from 660 practices throughout the UK. A total of 4,727,669 patients from 548 practices are currently active in the database. The CPRD GOLD population closely matches the age and gender distribution of the UK population as a whole. Mean follow-up is 6.9 years (median 5.0 years). Recorded data include demographic information, prescription details, clinical events, preventive care provided, specialist referrals, hospital admissions and their major outcomes. Data are retrieved by means of the READ classification system; READ codes are a coded thesaurus of clinical terms, which are the basic means by which clinicians record patient findings and procedures in health and social care IT systems across primary and secondary care (e.g. GP surgeries and pathology reporting of results). The Medcodes are the abbreviated terms which mean CPRD GOLD medical codes. Medcodes consisting of READ codes are used to enter medical diagnosis in the CPRD GOLD database.

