9.4.2. Data source for case ascertainment

First, the CPRD GOLD is based on data from GPs, while most auto-immune diseases would probably be diagnosed in specialist settings. Consequently, the number of auto-immune diseases, the quality of the information, and the diagnostic certainty might be lower compared to other databases that include hospital data only. In particular the specific information related to the onset of clinical symptoms, and radiological and biological data associated with the etiologic diagnosis of auto-immune diseases may not all be available in the CPRD GOLD database and associated resources. Besides, not all general practices participating to CPRD GOLD have consented to the linkage between CPRD GOLD primary care data and HES data (current linkage around 50% as of Q3 2012). Specific algorithms for each outcome of interest have been developed (Annex 5)

116239 (EPI-HPV-040 VS UK) Protocol FDA - EMA PASS Final Version 1

and available "free text" that is related to auto-immune disease diagnosis will be requested from CPRD GOLD, when needed.

Moreover, in a recent study by [Chao & Jacobsen, 2012], the authors recommended that expert case review of medical records is used in autoimmune safety studies, and case identification can be expanded by use of laboratory test results and other relevant measures in addition to specific ICD-10 diagnosis codes.

[figure not shown]
The ascertainment of the etiologic diagnosis and date of disease onset for all identified auto-immune diseases will be performed by a contract research organisation (CRO) to ensure the correct classification of each case. The CRO will review all subject data retrieved from CPRD GOLD including medcodes (including clinical, laboratory, and treatment files), the relevant "free text" and HES (including specific ICD-10 diagnostic codes), when available. They will assess whether the aetiology of the auto-immune disease is confirmed or not and whether the date of disease onset falls within the observation period of the study, which is one year after the reference date.

[figure not shown]
In the event that the aetiology or the date of onset could not be confirmed, a second review step will be conducted with an expert physician panel to reach an agreement about the case ascertainment, and, if they cannot reach an agreement, then the different clinical opinion of the experts will be listed. The experts will be blinded with regards to HPV vaccine exposure.

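### HES linkage feeds case confirmation, yet it is neither balanced between the female cohorts nor used in any stated model, so differential confirmation can be neither excluded nor seen

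*Protocol*

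**What the plan says.** **Matching.** Section 9.2.2: "All the unexposed subjects who matched exposed subject for age (birth cohort) and region (frequency matching) will be identified". It counts the cells: "This represents 234 combinations of birth cohort-region (18 birth cohorts and 13 regions in CPRD GOLD". Section 9.1.2 agrees that the cohorts are "matched for the age (age class of one year) and practice region identifier at reference date". Neither section includes practice or HES linkage.

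**HES.** Section 9.4.2 says that "not all general practices participating to CPRD GOLD have consented to the linkage between CPRD GOLD primary care data and HES data" and gives "current linkage around 50% as of Q3 2012". The same section lists HES, when available, among the records reviewed to confirm the diagnosis and date its onset. Only confirmed cases count in the primary endpoint (9.3.1).

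**Use of linkage status.** Section 9.3.3.1 extracts it: "HES information: Linkage to HES data". It does not appear again as an analysis variable:
- The baseline comparison in 9.7.4 names age, region and other vaccination.
- The primary model (9.7.5.1, 9.7.9.1) has exposure, age group and person-time.
- The sensitivity covariates in 9.7.9.1 are region, vaccination in the prior year and healthcare use in the prior year.

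**The protocol's own assurances.** Section 9.9 says that historical subjects can be linked as the exposed can, that HES access might raise the number of coded cases, and that the two male cohorts will show change over time. It adds that imperfect sensitivity leaves the risk ratio unbiased when the event is rare.

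**The concern.** The primary comparison assumes that a true case has the same chance of being confirmed in both female cohorts. HES is one source of confirmation, it is missing for about half of the database, and whether it is missing depends on the practice. Matching within region does not equalise it: "drawn from 660 practices throughout the UK" means about 51 practices per region on average (660/13), and they may differ in consent.

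There is also a possible route to imbalance. An exposed girl enters only with a dated Cervarix dose recorded in CPRD GOLD (9.2.4.1). A historical girl faces no such recording requirement (9.2.4.2). The documents do not show that this shifts the linked share, but nothing in the plan prevents or checks it.

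The assurances in 9.9 do not close the gap. The remark on sensitivity is right only when sensitivity is equal in the two cohorts. The remark that historical subjects can be linked equally concerns calendar time, not the mix of practices. Neither male cohort is selected on a recorded dose, so the male difference subtracted in 9.7.9.1 cannot cancel selection that acts on the exposed girls alone. The adjustment is also made only if the male cohorts differ significantly (9.7.5.1).

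**Working it through.** **1. The plan's own figures.** Matching cells: 18 × 13 = 234, as stated. Detectable relative risk at 50,000 per cohort, 80% power and two-sided 0.05: a pooled z calculation gives 1.64 at 100 per 100,000 and 1.96 at 50 per 100,000, against 1.6 and 2.0 in section 9.5.1. These are the yardstick for the size of any bias.

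**2. Formula.** Let a and b be the linked shares in the exposed and historical female cohorts, and k the probability that a true case is confirmed without HES relative to with HES. With a true ratio of 1, the expected ratio is

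IRR = [a + (1 − a)k] / [b + (1 − b)k].

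The documents give neither a, b by cohort, nor k. I take b = 0.50 from the database-wide figure and vary a and k.

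**3. A bound on a.** Table 2 (section 9.1.3) gives the completeness of HPV recording as q = 70.7/85.9 = 0.823 and 70.6/81.9 = 0.862. As a deliberate extreme, suppose that recording is all-or-none by practice and that overall linkage is 50%. Then a lies between (0.5 − (1 − q))/q and 0.5/q:
- q = 0.823: (0.5 − 0.177)/0.823 = 0.39 to 0.5/0.823 = 0.61
- q = 0.862: 0.42 to 0.58

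**4. Spurious IRR with a = 0.39 to 0.61 and b = 0.50.**

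| k | IRR, low a | IRR, high a |
|---|---|---|
| 0.5 | 0.93 | 1.07 |
| 0.7 | 0.96 | 1.04 |
| 0.9 | 0.99 | 1.01 |

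Worked case with unrounded a = 0.607 and k = 0.5: (0.607 + 0.393 × 0.5)/(0.5 + 0.5 × 0.5) = 0.8035/0.75 = 1.07.

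**5. Effect on the test.** With 50,000 person-years per cohort, the shift in z is ln(IRR)/√(1/λ0 + 1/λ1), where λ0 and λ1 are the expected cases. At 100 per 100,000 (λ0 = 50), an IRR of 1.05 gives 0.0488/0.198 = 0.247 and raises the false-positive rate from 5% to 5.7%. An IRR of 1.10, beyond the bound above, gives 7.8%. At 10 per 100,000 the same two ratios give 5.1% and 5.3%.

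**6. After balancing.** If a = b, the formula gives 1.00 for any k.

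**The case against.** The strongest case against is that the effect is small and partly guarded. Cases are first found by medcode algorithms (9.3.3.2), not by HES. Review also draws on clinical, laboratory and treatment records and on free text, and cases left unconfirmed go to an expert panel blinded to HPV exposure (9.4.2), so k = 0.5 may be pessimistic. The self-controlled case series tests both co-primary endpoints within the same girls, which removes practice differences that are fixed in time. Healthcare use is a sensitivity covariate. All of this stands and limits the size. But blinding does not supply missing HES records, and the case series does not protect the primary cohort estimate.

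It can also be said that a further covariate or subset analysis belongs in the statistical analysis plan. That would hold if the protocol were silent. It fixes the matching variables and lists the covariates, and matching cannot be repaired after selection.

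A reader might infer more than the documents support:
- That HPV recording is known to vary by practice. Sections 9.1.2, 9.1.3 and 9.9 describe under-recording for the database and for subjects. Only HES consent is attributed to practices. Step 3 of the working uses practice-level variation as an extreme, not as a fact.
- That practices which have left the database measure the problem. Section 9.4.1 says "A total of 4,727,669 patients from 548 practices are currently active in the database", against 660 in all, but gives no leaving dates. Turnover between the two periods would also act on the male cohorts, so their contrast captures part of it.
- That a much larger imbalance, such as 70% against 50% linked, is a fair scenario. It lies outside the 39-61% bound.

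**Conclusion.** The gap is real and modest. The protocol extracts HES linkage, relies on HES for confirmation, and then neither balances linkage between the female cohorts nor uses it in any stated model or listed baseline table. Differential confirmation therefore cannot be excluded, and an imbalance would not be visible from the stated outputs. The statement in 9.9 on sensitivity needs the condition that sensitivity is equal in both cohorts.

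Under the assumptions above (39-61% linked among the exposed, 50% among the historical girls, unlinked cases confirmed half as often), the spurious IRR is about 0.93-1.07, in either direction. A smaller penalty for missing HES narrows this range and a larger one widens it. Against a smallest planned detectable relative risk of 1.6, this alone would be unlikely to produce or hide the effects that the study is sized for. The documents do not show that any bias has occurred. The case for acting is that the remedy is cheap and the variable is already extracted.

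**What to change.** - Section 9.2.2: add HES-linkage status (yes/no) to the frequency-matching cells, at most 2 × 234 = 468, and merge sparse cells.
- Section 9.7.9.1: add HES linkage to the listed sensitivity covariates.
- Section 9.7.5.1: add one sensitivity analysis of both co-primary endpoints in HES-linked subjects only.
- Section 9.7.4: tabulate the linked share by cohort.
- Section 9.9: state that imperfect sensitivity leaves the ratio unbiased only if it is equal in the compared cohorts.

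Limiting the unexposed pools to practices with at least one exposed girl is not worth adding. With 65,000 exposed girls over 660 practices (about 98 each), it would probably exclude almost none.

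Cost: a change to the sampling program before selection, one covariate, one extra run and one table row. The downside is more and sparser matching cells and, with about half of subjects linked, a less precise HES-only analysis.

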9.2.4.1. Inclusion criteria for the exposed female cohort

Exposed females must satisfy ALL the following criteria at study entry:

- Female aged from 9 to 25 years at the reference date (01 September 2008 through 31 August 2010)
- Recorded in the CPRD GOLD for at least 12 months before the reference date
- The first dose of Cervarix received between 01 September 2008 through 31 August 2010, Full date (day/month/year) of Cervarix vaccination(s) available
- Subject defined as acceptable in CPRD GOLD

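### Sections 9.1.2 and 9.2.2 give matching rules that cannot both hold for the historical cohorts; followed literally, 9.2.2 makes historical subjects about 3 years younger than exposed subjects

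*Protocol*

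**What the plan says.** Protocol 9.1.2 states the intent. The cohorts are to be frequency "matched for the age (age class of one year) and practice region identifier at reference date". The reference date of an unexposed subject is "a date randomly selected among the reference dates of the exposed subjects and minus 3 years for the historical cohorts".

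Protocol 9.2.2 gives the working algorithm:

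- Candidates: "All the unexposed subjects who matched exposed subject for age (birth cohort) and region (frequency matching) will be identified".
- Cells: "This represents 234 combinations of birth cohort-region (18 birth cohorts and 13 regions in CPRD GOLD").
- Dates: "For the historical cohorts, the reference date is a random date between 01-SEP-2005 and 31-AUG-2007 (reference dates for exposed cohort – 3 years").
- Final draw: eligible subjects are "randomly selected in each of the combinations 'birth cohort-region' taking into account the distribution in the exposed cohort".

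Age at the reference date is calculated in 9.2.2, but it is not named as a stratum. The exposed dates come from 9.2.4.1: "The first dose of Cervarix received between 01 September 2008 through 31 August 2010". Section 9.2.4.2 requires historical females to be aged 9 to 25 at their own reference date in 2005 to 2007. The primary Poisson model (9.7.5.1 and 9.7.9.1) has one age term with two groups, [9-18] and [18-25]. The individual-disease Poisson model (9.7.6) has exposure and the person-time offset only.

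**The concern.** The historical female cohort is the comparator for the primary analysis, and frequency matching is the main control for age. Matching on birth cohort controls age only when both groups are indexed at the same calendar time. Here the historical index dates are 3 years earlier, so the same birth cohort means a different age.

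Several of the outcomes change in incidence through adolescence, so an age gap can produce a rate ratio away from 1 with no vaccine effect, or hide a real one. The historical male cohort would be shifted in the same way. The male contrast, meant to show changes in diagnosis and coding over time, would then also carry an age effect, and that contrast feeds the adjusted female model in 9.7.9.1.

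**Working it through.** **1. The protocol's own count.** 18 birth cohorts × 13 regions = 234, as stated.

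**2. The shift.** 01-SEP-2008 minus 01-SEP-2005 is 3.0 years, and 31-AUG-2010 minus 31-AUG-2007 is 3.0 years. Examples within one birth cohort:

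| Born | Age on 01-SEP-2008 | Age on 01-SEP-2005 |
|---|---|---|
| 01-SEP-1994 | 14 | 11 |
| 01-SEP-1996 | 12 | 9 |
| 01-SEP-1997 | 11 | 8 (not eligible) |

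For the concurrent males the windows coincide, so matching by birth cohort produces no such shift.

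**3. Size over the cohort.** Inputs are the Table 3 counts: 16 aged 9-10, 82,326 aged 11-15, 65,080 aged 16-20 and 866 aged 21-25, total 148,288. Assumptions: uniform age within each band, uniform dates within each two-year window, and the same birth-cohort distribution in both groups. A variant starts the 11-15 band at 12. By simulation:

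| | Band from 11 | Band from 12 |
|---|---|---|
| Mean age, exposed | 15.8 | 16.0 |
| Mean age, historical, nobody excluded | 12.8 | 13.0 |
| Historical matches under 9 | 12% | 5% |
| Overall gap, under-9s dropped and not replaced | 2.4 years | 2.8 years |
| Gap within the same births, after exclusion | 2.9 years | 3.0 years |
| Aged 18 or over, exposed / historical | 27% / 4% | 27% / 4% |

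**4. What the two-group covariate leaves.** After the under-9s are dropped, mean age among those under 18 is 14.3 exposed against 13.1 historical (14.7 against 13.0 in the variant). So 1.2 to 1.7 years of the gap remain inside the lower group.

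**5. Illustrations with no vaccine effect.**

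- Autoimmune thyroiditis, US females, 19.5 per 100,000 at 10-17 and 37.8 at 18-25. As a step at 18: exposed 0.731 × 19.5 + 0.269 × 37.8 = 24.4; historical 0.961 × 19.5 + 0.039 × 37.8 = 20.2; ratio 1.21. As a log-linear trend between band midpoints 8 years apart: (37.8/19.5)^(3/8) = 1.28 for a 3-year gap. Over the simulated ages the trend gives 1.23 to 1.28 crude, and 1.09 to 1.15 after the two-group covariate. Under the pure step, the covariate would remove all of it.
- Type 1 diabetes, UK females, 26.0 at 10-19 and 10.1 at 15-34, midpoints 10 years apart: (10.1/26.0)^(3/10) = 0.75. Over the simulated ages this gives 0.75 to 0.80 crude and 0.83 to 0.88 after the covariate. The direction depends on which rows are used: Table 1 also gives 15.3 to 25.9 at 0-14, which shows no fall up to the 10-19 figure.

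**6. Where the crude bias would count.** The model in 9.7.6 runs with more than 10 cases. At 65,000 person-years, thyroiditis would give about 65,000 × 24.4/100,000 = 15.9 exposed and 65,000 × 20.2/100,000 = 13.1 historical cases. It could therefore be fitted, with no age term.

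**The case against.** The best defence is that the wording is loose and the design is sound. The abstract and sections 9.1.1, 9.1.2 and 9.2.1 all speak of age matching. Section 9.2.2 itself names age as the variable, with birth cohort only in parentheses. The literal rule is partly unworkable, since it asks for 8-year-old controls. Section 9.2.2 also refers to a stepwise approach in Annex 5, a stand-alone document that may shift the birth cohorts. This stands as a condition on the result. It does not reconcile the text, because birth cohort also defines the cells, the date attribution and the final draw.

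There are safeguards. Age at reference date is compared between cohorts (9.7.4, 9.7.8.2), sensitivity analyses split at 18 and can include age (9.7.5.1), the male-adjusted model may subtract part of a like shift, and the self-controlled case series uses exposed girls only. These would show or soften the problem. However, the age comparison comes after selection with no remedy stated, the male adjustment applies only if the male contrast is significant, and Table 1 shows age gradients that differ by sex.

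Some stronger readings are not supported:

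- A reader might take 234 cells, rather than 17 ages × 13 regions = 221, as proof that no shift is applied. Eighteen birth cohorts remain eighteen whether or not they are shifted.
- A reader might cite 9.2.1 as a second promise of one-year classes for every cohort. It attaches those classes to the concurrent males only.
- A reader might extrapolate multiple sclerosis to a threefold ratio, (5.9/0.9)^(3/5) = 3.1. Those rates cover ages 15 to 24 from a source that Table 1 flags as probably incomplete, while 82,326/148,288 = 56% of vaccinees are aged 11-15. Even at 5.9 per 100,000, 65,000 person-years give about 4 cases.

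**Conclusion.** The contradiction is real and should be resolved before the unexposed cohorts are drawn. As written, 9.2.2 gives historical subjects of both sexes who are about 3 years younger within strata, and about 2.4 to 3.0 years younger overall. The overall figure rests on the Table 3 bands with uniform age within each, and on Annex 5 applying no shift.

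The consequence is confounding by age in the primary female contrast and in the male time contrast. The two-group covariate corrects it in part, and the individual-disease model does not correct it at all. Size and direction differ by disease.

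A reader might infer a definite upward bias in the two composite endpoints. Table 1 does not support a figure: uveitis and optic neuritis have a single rate for ages 9-26, several components have no rate by age, and a fall in diabetes could offset a rise in thyroid and bowel disease. The net ratio may be near 1, but such cancellation depends on case mix and is no safeguard.

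The reference-date wording is a secondary ambiguity. Section 9.1.2 draws from the exposed subjects' dates, while 9.2.2 describes a random date in a two-year window and then ties it in parentheses to the exposed dates. A seasonal bias might be inferred, but the documents give nothing from which to size it.

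**What to change.** In 9.2.2, define the strata and the final draw for all three unexposed cohorts as one-year age at reference date by region, to the exposed distribution. Equivalently, keep birth cohorts and state that the historical cohorts use those 3 years earlier. Restate the cell count only if the strata change; shifted birth cohorts still give 18 × 13 = 234.

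State one reference-date rule consistent with 9.1.2: drawn from the exposed subjects' dates, minus 3 years for the historical cohorts. Confirm that Annex 5 says the same.

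The cost is a wording change and a few lines of selection code. No new data are needed.
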